9.1 Data Handling After Cut-off Date

By its nature, data after cut-off may be incomplete and subject to further change and will not be used for summary statistics, statistical analyses, listings or imputations.

Stop dates are not affected by this rule, e.g., the stop date of an AE that starts prior to the cut-off, but stops after the date of cut-off, will not be changed.

These rules will be applied to all analyses performed for the IDMC meetings as well for the primary analysis. For the final analysis no cut-off date will be applied: the analysis will be performed only after all the data have been collected, fully cleaned and the database has been locked.

9.2 Study Day / Study Treatment Day

In this IAP, "study treatment" comprises tepotinib and osimertinib in the combination arm and indicates tepotinib only in the monotherapy arm; "study treatment component" will be used to refer to each study drug separately.

Day 1 is the day of the start of study treatment, the day before is Day -1 (no Day 0 is defined). Study day / Study treatment day is defined relative to Day 1.

Study treatment start date:

For each participant, the study treatment start date is the date of first administration of the study treatment (for the combination arm, it will be the earliest date between the two study treatment components; for the monotherapy arm it will be the date of the first administration of tepotinib).

Study treatment end date:

For each participant in the combination arm, the study treatment end date is the date of the last administration of the study treatment (for the combination arm, it will be the latest date between

29/94

the two study components; for the monotherapy arm it will be the last date of administration of tepotinib as monotherapy).

9.3 Definition of On-treatment Periods

Participants in the monotherapy arm will be allowed to switch to the combination treatment once PD is confirmed. The following on-treatment periods are defined in order to indicate which data will be used for the analyses.

Table 3.	On-treatment Periods
----------	-----------------------------

		Combination Arm	Monotherapy Arm - No Switch	Monotherapy Arm – Switch ^a
Period 1	Start	First dose of study treatment	First dose of study treatment	First dose of study treatment
	End	Last dose of study treatment + 30 days or the cut-off date or death, whichever occurs first	Last dose of study treatment + 30 days or the cut-off date or death, whichever occurs first	First dose of osimertinib ^b
Period 2	Start	NA	NA	First dose of osimertinib ^b
	End	NA	NA	Last dose of combination treatment ^c + 30 days or the cut-off date or death, whichever occurs first

a: Unless stated otherwise, data from Period 1 will contribute to tables, figures and listings whereas data from Period 2 to study discontinuation will only be listed.

b: Measurements collected on the day of the start of the combination treatment will be considered to belong to Period 1 unless clearly collected after the first administration of osimertinib. The same rule applies to adverse events.

c: The last dose of the combination treatment is considered as the last dose of tepotinib or osimertinib, whichever is later.

9.4 Definition of Baseline and Change from Baseline

In general, the last non-missing measurement prior to start of study treatment will serve as the baseline measurement for both periods (see Table 3).

If the assessment time of any pre-dose baseline assessments (as planned per protocol) and/or the time of initial dosing are unknown, but they are known to have been performed on the same day, it will be assumed that it was performed prior to dosing. Unscheduled assessments may be used in the determination of baseline; however, if the time of either the assessment or initial dose is missing, the unscheduled assessment will be considered to have been obtained after study treatment administration.

If a scheduled pre-dose measurement actually occurred post-dose, then the corresponding measurement will be analyzed similar to an unscheduled post-dose measurement.

Absolute and percent changes from baseline are defined as

absolute change = visit value - baseline value

percent change = 100 * (visit value – baseline value) / baseline value

9.5 Definition of Duration and 'time since' Variables

Durations in days will be calculated by the difference of start and stop date + 1, if not otherwise specified.

The time since an event (e.g., time since first diagnosis) will be calculated as reference date minus the date of the event, unless stated otherwise.

9.6 Conversion Factors

The following conversion factors will be used to convert days into weeks, months or years:

- 1 week = 7 days
- 1 month = 30.4375 days
- 1 year = 365.25 days

If height is recorded in inches, height (cm) = height (in) \times 2.54.

If weight is recorded in pounds, weight $(kg) = weight (lb) \div 2.2046$.

For the calculation of creatinine clearance: serum creatinine (mg/dL) = serum creatinine (umol/L) / 88.42.

9.7 Date of Last Contact

The date of last contact will be derived for participants not known to have died at the analysis cut-off using the latest complete date prior to or at the data cut-off date among the following:

- All participant assessment dates (blood draws (laboratory, PK, ctDNA, biomarker, PGx, etc.), vital signs, ECOG performance status, ECG, tumor assessments, quality of life assessments, pregnancy tests, echocardiogram);
- Start and end dates of anti-cancer therapies administered after study treatment discontinuation
- AE start and end dates
- Concomitant medication/procedures start and end dates
- Last known to be alive date collected on the "Subject Status / Survival Follow-up" eCRF page
- Tepotinib and osimertinib administration start and end dates
- Date of discontinuation on disposition eCRF pages (do not use this date if the reason for discontinuation is lost to follow-up)

Only dates associated with actual examinations of the participant will be used in the derivation. Dates associated with a technical operation unrelated to participant status such as the date a blood sample was processed will not be used. Assessment dates after the cut-off date will not be applied to derive the last contact date. This rule is to be applied to AE stop dates too: if an AE started before the cut-off date and ended after the cut-off date, only the complete start date will be used in the derivation of the last date of contact.

9.8 Time Window

For the purpose of Patient-reported Outcome (PRO) longitudinal analyses, time windows are defined as follows:

Analysis Cycle X Day 1 = Cycle X Day 1 target date +/- 21 days

In case of multiple PRO assessments in the analysis window, the one closest to the target date specified in the protocol will be used in the analysis; if two assessments are equally distanced from the target date, the earliest one will be selected. Both scheduled and unscheduled visits will be considered.

9.9 Imputation of Missing Data

Unless otherwise specified, all data will be evaluated as observed, and no imputation method for missing values will be used.

Imputed dates will be used for the calculation of durations.

In all participant data listings, imputed or censored values will be presented and imputed or censored information will be flagged.

Missing statistics, e.g., when they cannot be calculated, should be presented as "nd". For example, if n=1, the measure of variability (StDev) cannot be computed and should be presented as "nd".

Adverse events

Incomplete AE-related dates will be imputed as follows:

- If the AE onset date is missing completely, then the onset date will be replaced by the start of study treatment. If the end date or resolution date indicates that the AE has stopped before the start of treatment, this date will be used for imputation instead of the start of treatment date.
- If only the day part of the AE onset date is missing, but the month and year are equal to the start of study treatment, then the AE onset date will be replaced by the start of study treatment. For example, if the AE onset date is --/JAN/2015, and study treatment start date is 15/JAN/2015, then the imputed AE onset date will be 15/JAN/2015. If the end date or resolution date indicates that the AE has stopped before the start of treatment, this date will be used for imputation instead of the start of treatment date.

32/94

- If both the day and month of the AE onset date are missing but the onset year is equal to the start of study treatment, then the onset date will be replaced by the start of study treatment. For example, if AE onset date is --/---/2014, and study treatment start date is 19/NOV/2014, then the imputed AE onset date will be 19/NOV/2014. If the end date or resolution date indicates that the AE has stopped before the start of treatment, this date will be used for imputation instead of the start of treatment date.
- In all other cases the missing onset day or missing onset month will be replaced by 1.
- Incomplete stop date will be replaced by the last day of the month (if day is missing only), if not resulting in a date later than the date of participant's death. In the latter case, the date of death will be used to impute the incomplete stop date.
- In all other cases the incomplete stop date will not be imputed. If the stop date of an AE is after the date of cut-off this date will be kept.

Special cases: AEs may be split into multiple records if the toxicity grade changes (see Section 15.2.1 for more details). The end date of the previous record and the start date of the new record are expected to be the same. In the event that the month and year are indeed the same, but the day is missing, it will be imputed by 15. In case the imputed start date of the new record is after the end date of this same record, no imputation will be performed.

Prior osimertinib start and end dates

The following rules will be adopted to impute missing start or end dates:

- In case of partial start date with missing day, it will be imputed as the first day of the month.
- In case of partial end date with missing day, it will be imputed as the last day of the month or the day before the first dose of study treatment, whichever comes first.
- For both start and stop dates, if the month is missing or the date is completely missing, no imputation will be done.

Documented progressive disease

Incomplete dates for documented progressive disease as collected in the "Prior EGFR-TKI Drug Therapies Details", "Prior Osimertinib Therapies Details" and "Prior Anti-Cancer Drug Therapies Details" eCRF pages will be imputed as follows:

- If the day is missing, it will be imputed to the first day of the month.
- If the month is missing or the date is completely missing, no imputation will be done.

Previous and concomitant medication/procedure

For identification of previous or concomitant medications/procedures by period, no formal imputation will be performed on missing or incomplete dates. Rules presented in Table 4 and Table 5 will be used to define if a medication/procedure is considered as a previous, concomitant or both previous and concomitant medication/procedure.

If a medication/procedure could be allocated to both Period 1 and Period 2 due to missing start/stop dates, it will be allocated to Period 1. If a medication/procedure starts in Period 1 and continues in Period 2 it will also be allocated to Period 1.

End date of medication/procedure			Stopping rule	
Day	Month	Year		
UNK	UNK	UNK	After treatment start (ongoing)	
UNK	UNK	< Treatment start (year)	Before treatment start	
UNK	UNK	\geq Treatment start (year)	After treatment start	
UNK	< Treatment start (month and year)		Before treatment start	
UNK	\geq Treatment start (month and year)		After treatment start	
< Treatment start (complete date)		(complete date)	Before treatment start	
≥ Treatment start (complete date)		(complete date)	After treatment start	

Table 4.	Stopping rules for medication/procedure end dates
----------	--

UNK = Unknown

Table 5. Rules to define previous and/or concomitant medication/procedure

Start date of medication/procedure		Stopping rule (see Table 4)	Medication/procedure	
Day	Month	Year		
UNK	UNK	UNK	Before treatment start	Previous
UNK	UNK	UNK	After treatment start	Previous and concomitant
UNK	UNK	≤ Period 1 start (year)	Before treatment start	Previous
UNK	UNK	≤ Period 1 start (year)	After treatment start	Previous and concomitant
UNK	UNK	> Period 1 start (year) and \leq latest of Period 1 or Period 2 end (year)	After treatment start	Concomitant
UNK	≤ Period	l start (month and year)	Before treatment start	Previous
UNK	\leq Period 1 (month and year)		After treatment start	Previous and concomitant
UNK	 > Period 1 (month and year) and ≤ latest of Period 1 or Period 2 end JNK (month and year) 		After treatment start	Concomitant
≤ Period 1 start (date)		Before treatment start	Previous	
≤ Period 1 start (date)		After treatment start	Previous and concomitant	

Global Version ID: 78691_4195547_5992886

Start date of medication/procedure		Stopping rule (see Table 4)	Medication/procedure	
Day	Month	Year		
> Period 1 start (date) and and \leq latest of Period 1 or Period 2 end (date)		After treatment start	Concomitant	

UNK = Unknown

Death date

In general, missing or partial death dates will not be imputed. However, for the purpose of survival analyses, partially missing death dates will be imputed as follows: if only the day is missing, the death date will be imputed to the maximum of the (non-imputed) day after the date of last contact (see Section 9.7) and the 15th day of the month.

Tumor assessments

All investigation dates (e.g. X-ray, CT scan) must be completed with day, month and year.

If there are multiple scan dates associated with an evaluation, i.e., radiological assessments occur over a series of days rather than the same day, the choice of date of assessment could impact the date of progression and/or date of response. If there are multiple scan dates associated with an evaluation, the earliest of the scan dates associated with the evaluation will be used as the date of assessment.

If one or more investigation dates for an evaluation are incomplete but other investigation dates are available, the incomplete date(s) are not considered for calculation of the assessment date and assessment date is calculated as the earliest of all investigation dates (e.g., X-ray, CT-scan).

If all measurement dates for an evaluation have no day recorded, the 1st of the month is used.

If the month is not completed, for any of the investigations for an evaluation, the respective assessment will be considered to be at the date which is exactly between the previous and the following assessment. If both a previous and following assessments are not available, this assessment will not be used for any calculations.

Dates of subsequent anti-cancer therapy

For sensitivity analyses where the start of subsequent anti-cancer treatment is considered

Incomplete dates for the start date of subsequent anti-cancer therapies (drug therapy, radiation, surgery) will be imputed as follows and will be used for determining censoring dates for efficacy related sensitivity analyses:

• If only the day is missing, it will be imputed as the first day of the month unless it results in a date before the end date of study treatment. In that case, the incomplete anti-cancer therapy start date will be imputed as the end date of study treatment.

• If both the day and month are missing, the incomplete anti-cancer therapy start date will be imputed as the end date of study treatment if the subsequent therapy started on the same year as the end of study treatment; otherwise, day and month will be imputed as the 1st of January.

For duration of subsequent anti-cancer drug therapies

Incomplete dates of subsequent anti-cancer drug therapies will be imputed as follows:

- If only the day is missing in the start date, the same rule as for the sensitivity analysis described above will be applied.
- If only the day is missing in the end date, it will be imputed as the last day of the month.
- For both start and stop dates, if the month is missing or the date is completely missing, then no imputation will be done and the duration will be considered missing.

Nicotine consumption

Imputation will be used for the calculation of duration of consumption (years) only.

In case of missing month, it will be imputed as follows:

- Missing month of start date will be imputed as January
- Missing month of end date will be imputed as December

In case the start date is missing completely, the start date will not be imputed and duration will not be calculated.

In the case that the end date is missing completely (i.e. the participant is still using nicotine), in order to allow the calculation of duration, the end date will be imputed by the screening informed consent date.

As the day of the month is also needed to calculate the duration of consumption, the first day and last day of the month for the start date and end date will be used, respectively.

Disease history

Incomplete dates for disease history (e.g., initial diagnosis date, date of documented metastatic disease diagnosis) will be imputed as follows:

- If the day is missing, it will be imputed to the 15th day of the month
- If both the day and month are missing and the year is prior to the year of the first study treatment, the month and day will be imputed as the 1st of July
- If both the day and month are missing and the year is the same as the year of the first study treatment, the month and day will be imputed as the 1st of January

If the date is completely missing, no imputation will be performed.

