TEAEs are those events that started during the on-treatment periods (see Section 9.3), or before Period 1 and worsened during the on-treatment periods. This includes also AEs ongoing at baseline, which first improve under study treatment and then worsen irrespective of baseline. The rules defined in Table 10 will be used to assign TEAEs to the on-treatment periods. Any AE occurring before Period 1 and resolved before Period 1 or not worsening during the on-treatment periods will be included in the AE listings, but will not be included in the TEAE summary tables (unless otherwise stated). Adverse events with changes in toxicity grade are recorded as separate entries in the eCRF with associated end and start dates (start date equals end date of previous entry, supported in eCRF by 'AENEWID' in SUPPAE). Records of the same AE will be considered as one event in the analysis. These events will be kept as separate records in the database in order to maintain the full detailed history of the events. In AE listings, records that are part of the same AE will be grouped together and presented in chronological order. If the severity of the reported event worsens after start of treatment, the TEAE flag will be re-evaluated for the worse and the subsequent records as per the TEAE definition: once one record is considered treatment emergent, all the subsequent records will be considered treatment emergent too, even if starting after the ontreatment periods.

All analyses described in Sections 15.2.2 and 15.2.3 will be based on TEAEs belonging to Period 1, if not otherwise specified. The AE listings will include all AEs (whether treatment emergent or not). A flag will be added to indicate if the AE is treatment emergent and in which period.

Unless otherwise specified, TEAEs will be summarized by number and percentage of participants with the TEAE in the category of interest and sorted by primary SOC and PT in alphabetic order.

Each participant will be counted only once within each SOC or PT. If a participant experiences more than one AE within an SOC or PT for the same summary period, only the AE with the strongest relationship or the worst severity, as appropriate, will be included in the summaries of relationship and severity.

Table 10.	Assignment of TEAEs to the on-treatment periods

	TEAE in Period 1	TEAE in Period 2
Starts before Period 1 and worsens during Period 1	Х	
Starts before Period 1 and worsens during Period 2		Х

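### The SAP's day-15 rule for an undated AE grade change has no lower bound at first dose or at the previous record's start, so some on-treatment worsenings are dated before treatment and some records end before they begin.

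*SAP*

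**What the plan says.** SAP Section 9.9 has two rules for an AE date with only the day missing.

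- **Ordinary onset.** If the month and year match those of first dose, "then the AE onset date will be replaced by the start of study treatment". If the AE's end date shows that it was over before treatment, that end date is used instead.
- **Special case: records split at a grade change.** The end of one record and the start of the next should be the same date. "In the event that the month and year are indeed the same, but the day is missing, it will be imputed by 15". One exception follows: "In case the imputed start date of the new record is after the end date of this same record, no imputation will be performed".

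SAP Section 15.2.1 sends incomplete AE dates to Section 9.9 and makes the outcome depend on them: "TEAEs are those events that started during the on-treatment periods (see Section 9.3), or before Period 1 and worsened during the on-treatment periods". An earlier AE that shows no such change is kept out of the tables, the words for it being: "not worsening during the on-treatment periods will be included in the AE listings, but will not be included in the TEAE summary tables". Status also carries forward: "once one record is considered treatment emergent, all the subsequent records will be considered treatment emergent too".

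Protocol Section 8.3.1 starts AE collection at Prescreening consent, so AEs that begin before dosing are in the database.

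**The concern.** The special case fixes the date at mid-month and checks it against one thing only, the end of the new record. It does not check it against the first dose, as the general onset rule does, or against the start of the record being closed.

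The first omission affects a safety result. For an AE that began before dosing, the date of worsening alone decides whether it is a TEAE. If that date is set before Period 1, the worsening leaves the TEAE tables, including the Grade 3 or higher tables where the new grade qualifies. Low-grade symptoms that arise between consent and first dose and worsen on the study drugs are what the worsening clause is meant to catch. The second omission can give a record an end date earlier than its start.

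Elsewhere Section 9.9 does use lower bounds. A death date with a missing day takes the later of the 15th and the day after last contact. The start of subsequent therapy is not allowed to fall before the end of study treatment.

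**Working it through.** **Inputs.** The general onset rule, the day-15 rule and its exception (SAP 9.9); the TEAE definition and carry-forward (SAP 15.2.1); duration = stop − start + 1 (SAP 9.5).

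**1. Reproduce the SAP's own examples.** Under the general rule, onset --/JAN/2015 with first dose 15/JAN/2015 gives 15/JAN/2015. Onset --/---/2014 with first dose 19/NOV/2014 gives 19/NOV/2014. Both agree with Section 9.9.

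**2. Apply the special case.** An AE arises after Prescreening consent and before dosing. First dose is 20 January. The grade worsens on treatment in January, day unknown, and the new record ends on 10 February.

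- Day-15 rule: 15 January. The exception does not apply, because 15 January is before 10 February. The worsening precedes Period 1 and is not a TEAE.
- With the general rule's floor: 20 January, a TEAE.

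The exception can never rescue such a case. With first dose on day 16 or later, a record that starts on treatment also ends after the 15th.

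**3. Count the losses.** Let n be the month length, f the first-dose day and w the true worsening day, with f ≤ w ≤ n. There are n(n+1)/2 such pairs. A worsening is lost when f > 15. That covers k = n − 15 first-dose days and k(k+1)/2 pairs.

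| n | First-dose days with loss | Pairs lost | Share |
|---|---|---|---|
| 28 | 13 (46%) | 91 of 406 | 22.4% |
| 30 | 15 (50%) | 120 of 465 | 25.8% |
| 31 | 16 (52%) | 136 of 496 | 27.4% |

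The shares assume that all pairs are equally likely. For any single first-dose day the result is all or nothing: every such worsening is lost from day 16 on, and none up to day 15.

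**4. Count the errors in the other direction.** For worsenings truly before dosing (w < f) in a 30-day month there are 30 × 29 / 2 = 435 pairs. With f ≤ 15 the imputed date falls on or after first dose. That is 0 + 1 + … + 14 = 105 pairs, or 24.1%. It is an upper figure, because the exception removes records that ended before the 15th.

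**5. Previous record's start.** A record starts on 22 January and the grade changes in January, day unknown. The imputed end is 15 January, so the duration is 15 − 22 + 1 = −6 days. In a 30-day month, with the previous record starting on day s of that month and w > s, there are 435 pairs. Those with s > 15 number 14 + 13 + … + 0 = 105, or 24.1%, again if all pairs are equally likely. If that AE began on treatment, its first record is already treatment-emergent and the status carries forward.

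**The case against.** The best defence is that the 15th is a midpoint convention and errs both ways. That is correct. A reader might infer that the rule can only lower TEAE counts, but step 4 shows that it can also count pre-dose worsenings when first dose is on or before the 15th. The downward direction holds only relative to the general onset rule.

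Two other inferences are tempting and not supported:

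- That the 15th is always imputed. The rule requires matching month and year, and it is waived when the 15th is after the new record's end.
- That a 15th before the AE's own start removes treatment-emergent status. Carry-forward in Section 15.2.1 prevents this for an AE that began on treatment.

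The defence can also say that few records are exposed. Under Protocol Appendix 4, conditions present at the initial study visit that do not worsen are not AEs. A symptom already present at Prescreening that later worsens could well be entered as a new AE, which the general rule would then date. What remains is an AE that newly arose between consent and first dose, stayed open, and changed grade on treatment in the month of first dose with the day missing, where first dose was after the 15th. Imputed values and TEAE flags appear in the listings, queries are to be resolved before lock (SAP 6.3), and a later dated on-treatment worsening would bring the AE back as a TEAE. All of this limits the size. None of it supplies the missing bound.

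Finally, the sponsor may have meant the first-dose floor to cover split records too. The text does not say so, and a programmer following the special case would not apply it.

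**Conclusion.** The rule is wrong as written, in a narrow set of cases. With first dose on day 16 or later, a missing-day worsening that truly occurred on treatment in that month, in an AE that began before dosing, is dated before treatment and not flagged as a TEAE. This conflicts with the general onset rule in the same section. The conditional share is 22% to 27% if first-dose and worsening days are equally likely pairs; the documents do not support or contradict that assumption. The negative-duration problem is a separate data-integrity fault with no effect on TEAE counts.

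The documents do not say how many grade changes lack a day. Since several conditions must coincide, the number is probably very small, and a material change to the safety conclusions is not to be expected. The point is worth correcting because a stated rule gives a wrong result and the correction is nearly free.

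**What to change.** Replace the special-case sentence in SAP Section 9.9 with wording to this effect: if only the day is missing and the month and year agree, impute the latest of (a) the 15th, (b) the start date of the previous record and (c), if the month and year equal those of first dose and the new record did not end before dosing, the study treatment start date. Keep the existing exception: no imputation if the result is after the new record's end date. It should not become a cap at that end date, which would be a different rule.

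Check: the example in step 2 becomes 20 January, a TEAE. The record in step 5 ends on 22 January, with a duration of 22 − 22 + 1 = 1 day. Where first dose is on or before the 15th, the first-dose term changes nothing.

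The cost is one sentence and one line of code. TEAE counts may rise slightly, and some true pre-dose worsenings will be counted. On the 30-day grid, up to 435 − 105 = 330 further pre-dose pairs would be dated on treatment if their records stayed open past dosing. The general onset rule already accepts that conservative trade for ordinary AEs.
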